3.3.1 Population for Objective 1 Interviews

Target population: Families of adolescent girls, clinicians, immunization nurses, administrative staff, and school leadership (at the governmental level, key informants will include leadership within the KCCA and Ministry of Health).

Study population: Families of adolescent girls, clinicians, immunization nurses, administrative staff, and school leadership (at the governmental level, key informants will include leadership within the KCCA and Ministry of Health).

Accessible population: Families of adolescent girls, clinicians, immunization nurses, administrative staff, and school leadership (at the governmental level, key informants will include leadership within the KCCA and Ministry of Health).

3.3.2 Selection Criteria for Objective 1 Interviews

Inclusion criteria for interviews:

- School-affiliated participants must:
 - Be affiliated one of the identified KCCA schools (Appendix 26)
 - Be in leadership role at school (i.e. Senior Woman or Head Teacher title)
 - Be involved in HPV-vaccination efforts at school
- Government-Affiliated Participants must:
 - Be local or national government official involved in an immunization programs
- Caregiver participants:
 - Is the primary caregiver of adolescent girl aged 10-14 years who has not completed the HPV vaccination series
 - Resides in Kampala
 - Speaks English or Luganda
 - Have a phone in the household
 - Adolescent is willing to take part in interview

- Adolescent participants:
 - Is an adolescent girl aged 10-14 years
 - Have not completed the HPV vaccination series
 - Have a phone in the household

• Caregiver is willing to take part in interview Exclusion criteria:

- Those who are unable to consent/assent to the study
- Those unable to be interviewed at the affiliated study health centres

3.3.3 Study procedure for Objective 1 Interviews

Interviews will be conducted by trained research staff overseen by an experienced social scientist on our study staff. At the Kisenyi, Kawaala and Kiswa study sites, families of adolescent girls aged 10-14 who have not completed the HPV vaccine series will be given a consent form/information sheet by a member of our study team. Then, they will be asked if they have any questions and if they are willing to participate. After being read the consent/assent form, one willing adult participant who is the primary caregiver of the adolescent will be asked to sign the consent and the 10-14 year old adolescent girl will also be asked to give written assent. In the case of there being more than one eligible female adolescent between the ages of 10-14, we will give the opportunity to both adolescents to be interviewed. If two caregivers are present and willing to take part, we will select the primary caregiver who is usually responsible for the adolescent being vaccinated.

To increase reach, study staff will also call families of 10-14 year old adolescent girls who have not completed the HPV vaccine series and receive care at the study-affiliated healthcare centres about possible participation. If these families are interested, they will be asked to travel to their study-associated healthcare centre to be consented and participate in the study interview and their transport to and from the health centre will be reimbursed.

The interviews will be grounded in the general domains of the critical interpretive synthesis framework put forth by Phillips et al in their comprehensive systematic review of vaccination studies in LMICs. After obtaining informed consent, interviews will be conducted using a semi-structured interview guide by trained research assistants with experience in conducting

interviews with adolescent and their caregivers. The guide was developed based on the investigators' experience with HPV vaccination. Audio-recorded interviews will last 30-40 minutes. We will use open-ended questions with neutral probes to facilitate discussion and \encourage unbiased responses. In addition, rather than leading the interview based on a predetermined hypothesis, we will allow the concepts to emerge inductively.

We will seek to interview 30 caregiver and adolescent dyads/triads, but will use an iterative data collection and analysis approach and continue data collection until data saturation is reached (e.g. no new themes arise from the data). Eligible criteria are outlined as above. Adults and adolescents will be interviewed concurrently, but separately to facilitate comfort and encourage honest answers. Family interviews will concentrate on text message reminder content, focusing on the attitudes, perceived norms and perceived control that may affect intent to vaccinate in the Phillips et al model. We will also assess desired message timing and phrasing. Additionally, we will assess if families want for only the caregiver or the caregiver plus adolescent to receive the messages.

At the health centres/clinics, we will interview clinicians caring for 10-14 year olds, immunization nurses, administrative staff, and medical leadership (n=12). We will purposefully sample schools from the list of KCCA health centre-affiliated schools included in Appendix 26, focusing on two per division each of which represent a different student demographic composition. At the study-affiliated schools, we will interview up to two people per school including the headmasters and staff involved in Child Days Plus/HPV vaccination. Interviews will include content discussions regarding experiences with families' vaccine knowledge and attitudes as well as community access and facility readiness factors from the Phillips et al model in order to align reminder content and timing with current processes. Interviews will take place in person at the facilities in which the participant works, or another decided upon location.

In addition, local and national government officials, including KCCA and MOH leadership involved in immunization programs, will also be interviewed with focus on access and readiness from the Phillips et al model and an eye towards sustainability (n=4). Interviews will take place in the leadership offices after written informed consent is obtained. We will interview the KCCA Directors of Education and Social Services, and of Public Health and Environment as well as the City Manager of Epidemiology and Surveillance. These individuals together oversee vaccination at the KCCA- affiliated schools, health centres, and immunization posts and in Kampala overall. At the MOH, we will interview the Program Manager of UNEPI.

During the process of data collection, COVID-19 risk management procedure (Appendix 24) will be followed to protect the health and safety of study participants and researchers.

3.3.4 Data management and analysis

Individual interviews will be transcribed verbatim from audiotapes and translated, as appropriate. Our qualitative lead and their team will review all transcriptions and conduct coding independently. Transcripts will be analyzed using immersion and crystallization process and thematic analysis, which are standard methods of qualitative analysis. Analyses will follow a systematic, iterative process in which transcripts will be independently read for familiarity with content. General thematic domains and codes will be identified, and then transcripts will be systematically and independently coded line-by-line by two team members. The coding scheme will remain flexible and open to accommodate expansion as the teams agree on new codes. Double coding of all data will occur to facilitate reliability. Coding inconsistencies will be reviewed and resolved during meetings with the research team. Thematic analyses will be facilitated by the use of NVivo software. Summaries of coded texts and comparative analyses will be discussed with the investigatory team who were not involved with the coding, as well as outside experts, to obtain validation. The themes identified through the qualitative analysis will be used to guide the construction of the text (and parallel phone) messages that will be pre-tested in Objective 2.

3.4 Objective

- **Objective 2a:** To develop HPV vaccine reminders with caregivers and their adolescent girls in Kampala.
- **Objective 2b:** To pretest HPV vaccine reminders with caregivers and their adolescent girls in Kampala.

3.4.1 Study procedure for Objective 2a message development

We will design the reminders using the information gathered under Objective 1 to identify the themes, content, timing and framing of the SMS reminders. We will also use content gathered during our previous studies described above, the relevant literature, and the team's expertise in text messaging, HPV vaccination, adolescent medicine, health literacy and community engagement. The same message content and timing will be used for those opting for voice reminders. The messaging will be behaviorally-informed with the framing based on findings from participants from Objective 1. Possible examples include "loss-frame" messages that focus on the negative consequences of an adolescent not being vaccinated, and/or "gain-frame" messages that focus on what can be achieved through vaccination. Messages may also include social comparisons that capitalize on social desirability bias in completing the HPV vaccine series, contigent on if this is found to be motivating to families based on the Objective 1 responses. Other messages may highlight doctor recommendations if Objective 1 respondents relay that this may motivate others.

The study team will design the messages. First, they will identify the key content, timing and framing for each message in the series as above. The project coordinator will then design the messages. The team will then iteratively revise the messages, keeping the text within the 160-character count and paying attention to reading level, as assessed by the Flesch–Kincaid readability test. The final draft messages will first be designed in English then will be forward translated from English into Luganda by an independent professional translator and then reverse translated by a second independent professional translator from Luganda into English. All the while, translators will ensure proper linguistic and cultural equivalence, following procedures adapted from guidelines for translating health services research measure. The two versions, the original English and the reverse-translated English, will then be compared by the study team.

3.4.2 Population for Objective 2b message pretest

Target population: Families at the adolescent clinics, KCCA health centres, immunization posts, and families of children registered at the affiliated schools.

Study population: Families at the adolescent clinics, KCCA health centres, immunization posts, and families of children registered at the affiliated schools.

Accessible population: Families at the adolescent clinics, KCCA health centres,

immunization posts, and families of children registered at the affiliated schools.

3.4.3 Selection Criteria for Objective 2b message pretest

Inclusion Criteria

To receive take part in this pre-testing, one must:

- Caregiver participants:
 - Is the primary caregiver of adolescent girl aged 10-14 years who has not completed the HPV vaccination series
 - Resides in Kampala
 - Speaks English or Luganda
 - Have a phone in the household
- Adolescent participants:
 - Is an adolescent girl aged 10-14 years
 - Have not completed the HPV vaccination series
 - Have a phone in the household
 - Caregiver is willing to take part in the pretest

Exclusion criteria

- Those who are unable to consent to the study
- Those unable to be interviewed at the affiliated study health centres
- Participation in Objective 1 study activities

3.4.4 Study procedure for Objective 2b message pretesting

We will show/read the designed messages with caregivers and adolescent to identify issues with clarity and persuasiveness. Using methods previously utilized by members of the study team, the project coordinator will purposefully sample families meeting criteria a above from the waiting rooms at the adolescent clinic and KCCA health centres. Families will be consented/assented as outlined in objective 1. After obtaining informed consent, the project coordinator will share the proposed messages and ask the caregiver to relay back, in their own words, what the message means to them in order to assess clarity. S/he will then ask families about the level of persuasiveness as well as any problems or suggested changes. Messages will be updated in an

iterative process until no new message changes are made. Based on our previous work, we anticipate needing 20 dyads (with representation by language and site).

3.4.5 Data management and analysis

Final messages will be reverse translated from Luganda and team members will review to make sure that the content is the same between the messages in the two languages. We will also map the final messages back to the factors of the critical interpretive synthesis framework related to attitudes, perceived norms and perceived control, as well as access.

3.5 AIM 3: To pilot assess the impact and feasibility of vaccine reminders on HPV vaccination

3.5.1 Population

Target population: Families of adolescent girls who visited any of the following health centers: Kisenyi HC IV, Kiswa HC III, or Kawaala HC III.

Study population: Families of adolescent girls who visited any of the following health centers: Kisenyi HC IV, Kiswa HC III, or Kawaala HC III.

Accessible population: Families of adolescent girls who visited any of the following health centers: Kisenyi HC IV, Kiswa HC III, or Kawaala HC III.

3.5.2 Selection Criteria

To receive messages one must:

- Be an adult parent of an adolescent girl aged 10-14 years
- Reside in Kampala and/or the surrounding districts
- Be affiliated with the study sites (care or school)
- Speak English or Luganda
- Have a cell phone with text messaging capability
- Must have ability to consent.

Exclusion Criteria:

- Parenting adult speaks other language than English or Luganda only
- Parenting adult already enrolled in the study for another child
- Participation in Objective 1, 2a/2b study activities

3.5.3 Study procedure

We will recruit eligible participants from the sites outlined in Aim 1 and 2. This includes health centres overseen by the Kampala Capital City Authority (KCCA), as well as the associated schools and immunization posts in the community. In addition, we will also recruit at the

Makerere/Mulago/Columbia Adolescent Health Clinic at Mulago National Referral Hospital, the teaching hospital for Makerere University College of Health Sciences.

For those vaccinated through clinic sites: Families will be recruited multiple ways. First, families who are interested can enroll directly at the health centre at the times research staff are on-site, possibly at the time they are being evaluated for another health condition and are not receiving the vaccine that day. Second, if research staff are not on-site, providers and nursing staff at the study sites will ask families permission to provide the research staff with their contact information to reach out to them to explain the study and if interested to meet with them to enroll them into the study.

For those vaccinated through community immunization posts: Village health workers who already work in each village will be mobilized to approach households with 10-14 year olds who are in need of vaccination (have not yet been vaccinated or who have initiated but have not completed the series) to identify those who would be interested in the study. Research staff will contact those who are interested, as above. The use of village health workers has been previously successful for both immunization campaigns and other research studies.

For those vaccinated through the Child Days Plus: Girls will be given an information sheet and the study contact number to bring home to their parents. We would get permission from the schools to call families back as above.

We will enroll only one child per family; if more than one is eligible, one will be randomly selected. For the pilot feasibility trial, we will enroll families of girls who are in need of either the first or second dose, with an outcome of receipt of next needed dose. Due to the need to complete the pilot feasibility trial quickly, we will only enroll those in need of the second dose if their next dose is due strictly between 8-20 weeks from enrollment. We will seek written consent from caregivers. We will seek written assent from adolescents of consented caregivers given instead. At enrollment, parents will be verbally administered a demographic and HPV vaccination knowledge and attitude survey.

After enrollment, the Ugandan project coordinator will randomize families into intervention vs. usual care arms (1:1 ratio) stratified by enrollment site, parental language (English or Luganda), and dose due (1st or 2nd) using a randomization module. Research staff will not know the study assignment during enrollment. The outcome assessor and analyst will remain blinded to arm assignments.

Families who report on the demographic survey their highest degree of schooling as P7 or below will be asked at enrollment if, in the case they are randomized to the intervention, they would prefer a voice reminder in lieu of texts; such reminders would include the same content, timing and interactivity as the texts. While in Kampala only 2.1% of women and 0.5% of men have no formal education, 17.6% of women and 17.1% of men completed only some primary school.31 Similarly, families whose daughter is returning to a boarding school and are enrolled at the Adolescent Clinic, health centres, or immunization post will be asked if, in the case they are randomized to the intervention, they want messages sent timed for the next school break. Alternatively, they can select the timing used for those not at boarding school. If the special timing is selected, we will account for the minimal interval between doses (for those in need of a second dose). Intervention-arm families enrolled through Child Days Plus will be sent their series prior to the next Child Days Plus event at their child's school or before any other special immunization day events, if the school holds one.

Intervention, Text Message Target, Content and Frequency:

For those families randomized to the intervention arm: Based on our previous studies as well as the full country HPV vaccine evaluation highlighting the parents involvement as vaccine decision makers, we plan for the messages to be targeted to the parent, unless in Aim 1 families suggest that girls should also receive the message. All text messages are automated and will be sent in English or Luganda based on parental preference.

The message sequence consists of 5 weekly, main message reminders beginning 5 weeks before the

HPV vaccine dose due date, followed by a series of 2 primary booster messages.(Figure 3). This is based on our previous studies that showed that the median number of messages needed to come in for a vaccine was 5. If enrollment happens more than 4 weeks before the main messages are due to

start, engagement messages will be sent monthly until main messages start. The due date for the vaccine will depend on whether the first (initiation) or second

(completion) dose is due and the enrollment site.

For those who need to initiate vaccination and are:

- *Recruited as part of the school-based program*, the due date will be defined as the next Child Days Plus
- *Recruited in health centre and not in boarding school*, the due date will be defined as 5 weeks after message initiation
- *Recruited in health centre and are in boarding schools,* the due date will be the next school break
- *Recruited in the community*, the due date will be defined as the next HPV vaccination day at the community immunization post that is at least 5 weeks after message initiation

For those who need to complete the vaccination series and are:

- *Recruited as part of the school-based program*, the due date will be defined as the next Child Days Plus
- *Recruited in health centre and not in boarding school*, the due date will be defined as 6 months after the date of the first dose (which is the recommended interval between doses)
- *Recruited in health centre and are in boarding schools,* the due date will be the next school break that is a least 5 months after the date of the first dose, which is the minimal allowed interval between doses
- *Recruited in the community*, the due date will be defined as the next HPV vaccination day at the community immunization post that is at least 5 months after the date of the first dose

Messages will focus on when/where to go for the next dose, and will include educational information identified in Aim 1. Messages will be different for those who need the first dose (initiation) and 2nd dose (completion). We will also include an interactive text message allowing participants to ask for and receive more information according to their specific needs, and receive an automated response with information on that subject. For those still unvaccinated, booster

messages will be sent bi-weekly for one month and then monthly until the end of the 6 month observation period for each individual during the pilot trial. Sites will be visited every 2-4 weeks to abstract data; we will stop messages for those already vaccinated. HPV registers for schools are generally kept with the affiliated KCCA health centre immunization nurses. For families of those unvaccinated who were first vaccinated at Child Days Plus will receive booster messages directing them to bring their daughter to the KCCA health centre affiliated with their school (who conducts their Child Days Plus outreach) as they will have missed the school vaccination day.

Usual Care arm: Families randomized to the *usual care arm* will not receive text message vaccine reminders.

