2.0 Literature Review

Completion rates of HPV vaccination in Uganda are low. The national HPV vaccination program in Uganda began in November 2015,¹⁴ and targets girls who are 10 years old.¹⁵ In Kampala, the *school-based* program is to be delivered during every health facility and outreach immunization session, but intensified during Child Days Plus- month-long outreach sessions held two times a year in April and October, or whichever months they will be held during the course of the study. The *community-based* program occurs throughout the year at health facilities- overseen by city authorities or health institutions.

Not all adolescents who receive the first dose of HPV vaccine receive the second dose they need to complete the series. Furthermore, of those who do receive the second dose, many do not receive it within the recommended 12 months, resulting in more days at risk. In two previous national surveys, 72% and 83% of girls assessed initiated vaccination, but only 39% and 27% of them, respectively, completed the series.¹⁶ While coverage rates have gone up in some areas of Uganda, in Kampala City currently only 29% of girls in the target age range have received two doses of the vaccine.¹⁷ Similarly, at an adolescent clinic (*study site*) in Kampala, of the girls aged less than 14 years old who initiated vaccination between November 2015 and July 2017, only 30.2% completed the series within 6 months and 36.5% within 12 months—and only 69.8% completed the series at all.¹⁸ At three local health centres and affiliated schools (*study sites*), average completion rates are even lower, ranging from 10.5% to 40.5% of those who initiated.¹⁷ The current rate of completion HPV2 is 12%.¹⁹

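### The school route to dose 2 has no minimum interval after dose 1, so some intervention families can be prompted, and scored as successes, before the protocol's 5-month minimum

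*Protocol*

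**What the plan says.** Protocol section 3.5.3 limits second-dose enrolment by the time still to run: "we will only enroll those in need of the second dose if their next dose is due strictly between 8-20 weeks from enrollment". For girls who need to complete the series, the due date then depends on where they were recruited:

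- Health centre, not boarding: "the due date will be defined as 6 months after the date of the first dose".
- Health centre, boarding: the first school break no sooner than 5 months after dose 1, "which is the minimal allowed interval between doses".
- Community: the next vaccination day at "the community immunization post that is at least 5 months after the date of the first dose".
- School-based programme: "the due date will be defined as the next Child Days Plus". This is the same definition as for girls due their first dose, who need no interval.

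The same section has intervention families enrolled through Child Days Plus receive their messages ahead of the next round at the school "or before any other special immunization day events, if the school holds one". Its one explicit safeguard, "If the special timing is selected, we will account for the minimal interval between doses", belongs to the boarding-school timing option, which is offered to families enrolled at the adolescent clinic, a health centre or an immunization post.

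In the SAP (Outcome Variables), outcome 2 is Yes for any dose 2 given fewer than 168 days after enrolment. Outcome 3 applies the same rule to the next needed dose. Neither these nor the time-to-event outcome sets a minimum gap from dose 1.

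**The concern.** The protocol states a minimum interval between doses and builds an interval into three of its four second-dose routes. On the school route nothing in the text stops the reminder series from pointing a family to a date before that minimum.

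Two things could follow, both arising from messages that only the intervention arm receives. If the early dose is given, it counts towards the 24-week outcomes, the relative risk and the number needed to treat, although the protocol would not allow it. If the vaccinator declines, the family has made a wasted trip and the main messages have been spent before the dose could be given; the later boosters soften that loss but carry no interval check either. The first inflates the dose 2 effect and the second dilutes it. Section 3.5.4 wants that effect size for planning the full trial.

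**Working it through.** The plan gives no figure on this point to reproduce. The sample size (77 per arm, hazard ratio 1.67) neither depends on it nor changes with it. The check is date arithmetic.

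**Inputs.** Enrolment window of 8 to 20 weeks, due dates by route, 5-month minimum, main messages starting 5 weeks before the due date (section 3.5.3). Child Days Plus held as month-long rounds in April and October, or in other months if moved (section 2.0). Success if the dose comes before day 168 from enrolment (SAP). Five months = 152 days = 21.7 weeks; 6 months = 26 weeks.

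**Step 1: gap at the due date.** Let a be weeks since dose 1 at enrolment and w weeks from enrolment to the due date, with w between 8 and 20. The gap between doses is a + w.

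- Health centre, not boarding: the gap is fixed at 26, so a runs from 26 − 20 = 6 to 26 − 8 = 18 weeks.
- Boarding and community: the gap is at least 21.7 by definition.
- School: no condition on a. With a = 0 the gap is 8 to 20 weeks, always short. With a = 4 it is 12 to 24, sometimes short. With a = 14 it is 22 to 34, never short. The lower limit is just over 8 weeks, which is up to 21.7 − 8 = 13.7 weeks short.

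**Step 2: does the calendar supply the missing floor?** For a girl given dose 1 in one round and due in the next, the shortest gaps are 31 October to 1 April = 152 days and 30 April to 1 October = 154 days. Each is one day past 5 calendar months. The longest gap is 1 April to 31 October = 213 days. On the stated calendar she is always at or above the minimum.

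**Step 3: where the calendar does not help.**

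- *Dose 1 off-round.* Section 2.0 says the school-based "program is to be delivered during every health facility and outreach immunization session, but intensified during Child Days Plus", so doses outside the rounds are possible. Example: dose 1 on 1 July, recruited through the school the same day, round on 1 October. The due date is 92 days (13.1 weeks) away, inside the window. Messages start on 27 August, 57 days after dose 1. Five months is not reached until 1 December. At the extreme, dose 1 and enrolment on 5 August with a 1 October round give 57 days (8.1 weeks).
- *A special immunization day.* A girl given dose 1 at a round can be messaged for a special day less than 5 months later; the clause sets no interval.
- *Moved rounds.* If round starts were 5 months apart (an assumption), month-long rounds would give gaps of about 4 to 6 months.

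**Step 4: effect on scoring.** The July girl's dose on 1 October is day 92 from enrolment, so outcomes 2 and 3 are Yes. Each such dose adds at most 1/77 = 1.3 points to the intervention arm's combined uptake. It is a maximum because she might otherwise have had a valid dose in time: 5 months is day 153, which leaves days 153 to 167 (1 to 15 December). On outcome 2 the denominator is the dose 2 girls in the arm, a number the plan does not give.

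**The case against.** The case on the other side is good on reach. Section 3.5.3 describes school recruits as girls vaccinated through Child Days Plus, and for them the April and October calendar does the work of a floor. A girl who started at a clinic or post would normally be recruited there, where an interval applies. Off-round school starters rest on a general description of the programme in the literature review. The special-day clause also serves first-dose girls, and no document says how often such days occur. All of this stands and limits the problem to a minority of school recruits. It does not close the gap, because the due-date bullets sort girls by where they were recruited, not by where or when dose 1 was given.

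It is also fair to say that receipt of the next dose is a legitimate outcome, that the scoring rule is the same in both arms, and that the pilot's main focus is feasibility. The 6-month interval in the Operational Definitions defines completion, which the SAP outcomes do not claim to measure. These points are why a sensitivity analysis is an acceptable alternative to changing the outcome.

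A reader might infer that the 8-to-20-week window is itself the fault. It is not: it runs to a due date which, on three routes, already contains the interval from dose 1. A reader might also infer that school girls in general are called too early; Step 2 shows otherwise.

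**Conclusion.** The point holds in a limited form. The school second-dose due date and the special-day option lack the interval that every other second-dose route has, so a school-recruited girl with an off-round dose 1, a special day or moved rounds can be prompted before 5 months, in the extreme just over 8 weeks after dose 1. Only the intervention arm is prompted, and the SAP would score the resulting dose as a success.

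It is tempting to go further and put a share on the girls affected, or to say that the dose 2 effect is materially biased. The documents do not support either. They give no count of off-round starters or special days and no dose 2 denominator, they do not say whether vaccinators would give or refuse an early dose, and any share would depend on the assumed day within a month-long round. What can be stated is the ceiling of 1.3 points per early dose on the intervention arm's combined uptake. The net effect may be smaller, and the direction is uncertain if early doses are refused. This is a cheap improvement, not a threat to the pilot.

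**What to change.** In protocol section 3.5.3, give the school completion bullet the condition that the community bullet already has: the next Child Days Plus no sooner than 5 months after dose 1. Apply the same condition, for second-dose girls, to the sentence on other special immunization days.

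In the SAP, list by arm every dose 2 given less than 5 months after dose 1. In outcomes 2 and 3, score dose 2 as Yes only if it comes at least 5 months after dose 1. If the sponsor prefers to keep receipt of any dose as the outcome, report the 5-month version as a sensitivity analysis. The Kaplan-Meier analysis, which the SAP bases on the same 24-week variables, should follow whichever rule is chosen.

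The cost is one phrase and one clause in the protocol, one condition in two outcome variables, and one listing. The dose 1 date is already needed for the other routes, and the sample size is unchanged. The downside is that a few school second-dose girls would have their due date moved to a later round, fall outside the 8-to-20-week window and not be enrolled.
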